### **Cumulative dose**

Cumulative dose for any component of study treatment is defined as the total dose of the medication given during the study treatment exposure.

Cumulative dose will be summarized using descriptive statistics by treatment arm for each component of study treatment. For subjects who do not receive any drug the cumulative dose will be set to zero.

The cumulative dose is defined according to the type of dosing schedule and is calculated from the DAR eCRF.

The cumulative dose for canakinumab and pembrolizumab is defined based on the days when the subject is assumed to have taken a non-zero dose during dosing periods.

### **Dose intensity and relative dose intensity**

**Dose intensity (DI)** for subjects with non-zero duration of exposure is defined as follows:

DI (dosing unit / cycle) = Actual Cumulative dose (dosing unit) / (last dose date-first dose date+dose interval) \*21 (days/cycle).

For canakinumab, dose interval is 21 days. For pembrolizumab, dose interval is 21 days.

For subjects who did not take any drug the DI is by definition equal to zero.

**Planned dose intensity (PDI)** is defined as follows:

- for canakinumab, PDI is 200mg/cycle;

- for pembrolizumab, PDI is 200mg/cycle.

**Relative dose intensity (RDI)** is defined as follows:

RDI = DI (dosing unit / cycle) / PDI (dosing unit / cycle) \* 100%.

For canakinumab and pembrolizumab, the dosing unit is mg. DI and RDI will be summarized for each of the study drug (canakinumab and pembrolizumab) by treatment arm using descriptive summaries. In addition, categorical summary of RDI for each study drug will be presented. The number of administrations of each study drug component of the study treatment will be summarized.

### **Dose interruptions or permanent discontinuations**

The number of subjects who have dose interruptions and permanent discontinuations and the corresponding reasons, will be summarized separately for each of the study treatment components. The duration of the interruption will also be summarized by descriptive statistics.

‘Dose interrupted’, and ‘Dose permanently discontinued’ fields from the Dosage Administration CRF pages (DAR) will be used to determine the dose interruptions, and permanent discontinuations, respectively. The corresponding fields ‘Reason for dose interrupted’ and ‘Reason for permanent discontinuation’ will be used to summarize the reasons.

For the purpose of summarizing interruptions and reasons, in case multiple entries for interruption that are entered on consecutive days with different reasons will be counted as separate interruptions. However, if the reason is the same in this mentioned multiple entries on consecutive days, then it will be counted as one interruption.

### **2.4.2 Prior, concomitant and post treatment therapies**

#### **Post treatment anti-cancer therapy**

Given neoadjuvant setting, no prior antineoplastic therapies are allowed.

Antineoplastic medications since discontinuation of study treatment will be summarized by Anatomical Therapeutic Chemical (ATC) class, preferred term and treatment arm.

Separate listings will be produced for anti-neoplastic medications, radiotherapy, and surgery since discontinuation of study treatment.

Anti-neoplastic medications will be coded using the WHO Drug Dictionary (WHO-DD). Details regarding WHO-DD version will be included in the footnote in the tables/listings.

The above analyses will be performed using the FAS.

#### **Concomitant therapy**

Concomitant therapy is defined as all interventions (therapeutic treatments and procedures) other than the study treatment administered to a patient coinciding with the study treatment period. Concomitant therapy include medications (other than study drugs) starting on or after the start date of study treatment or medications starting prior to the start date of study treatment and continuing after the start date of study treatment.

Concomitant medications will be coded using the World Health Organization (WHO) Drug Reference Listing (DRL) dictionary that employs the WHO ATC classification system and summarized by lowest ATC class, preferred term and treatment arm using frequency counts and percentages. Surgical and medical procedures will be coded using MedDRA and summarized by SOC, preferred term and treatment arm. These summaries will include:

1. Medications starting on or after the start of study treatment but no later than 130 days after start of last dose of study treatment and
2. Medications starting prior to start of study treatment and continuing after the start of study treatment.

All concomitant therapies will be listed. Any concomitant therapies starting and ending prior to the start of study treatment or starting more than 130 days after the last date of study treatment will be flagged in the listing. The safety set will be used for all concomitant medication tables and listings.

## **2.5 Analysis of the primary objective**

The primary objective of the study is to assess the MPR rate ( $\leq 10\%$  residual viable tumor) per central review at the time of surgery in canakinumab alone and in combination with pembrolizumab treatment arms.

### **2.5.1 Primary endpoint**

The primary endpoint is MPR rate, defined as the percentage of subjects with  $\leq 10\%$  residual viable cancer cells. MPR will be assessed in FAS per central review.

### **2.5.2 Statistical hypothesis, model, and method of analysis**

The primary estimand will be described by the following five attributes:

1. The **target population** is defined as all randomized patients who are histologically confirmed NSCLC stage IB-IIIA (per AJCC 8th edition), deemed suitable for primary resection by treating surgeon, except for N2 and T4 tumors.
2. The **primary variable** is the percentage of subjects with a major pathological response (defined as  $\leq 10\%$  residual viable cancer cells per central review). Any patient who has  $>10\%$  residual viable cancer cells, or starts new antineoplastic therapy prior to surgery, or does not have the surgery performed, or has the surgery performed but with unevaluable MPR result, is considered as a non-responder.
3. The **study treatment** is canakinumab as monotherapy or in combination with pembrolizumab.
4. The **intercurrent events** of interest in this study are: start of new antineoplastic therapy prior to surgery and discontinuation of study treatment prior to surgery. These intercurrent events will be addressed as follows:
  - a. **Start of new antineoplastic therapy prior to surgery:** subject will be considered as non-responder (composite strategy)
  - b. **Discontinuation of study treatment prior to surgery:** subject will be included in the analysis regardless of this intercurrent event (treatment-policy strategy).

5. The **summary measure** is MPR rate with its corresponding two-sided exact binomial 95% confidence interval ([Clopper CJ and Pearson ES \(1934\)](#). [The use of confidence or fiducial limits illustrated in the case of the binomial. Biometrical, 26, 404-413.](#)) in canakinumab alone arm and canakinumab in combination with pembrolizumab arm.

A MPR of approximately 20% can be achieved using chemotherapy ([Pataer 2012 et al](#)). For canakinumab alone arm, a 10% absolute improvement in the MPR to 30% is considered a clinically meaningful minimum improvement in this study population. Therefore, proof of efficacy in canakinumab alone arm will be declared if both of the following conditions are met:

- the mean of the posterior distribution of MPR is at least 30% and
- the posterior probability that the MPR is  $\geq 20\%$  is at least 90%

For the combination of canakinumab and pembrolizumab treatment arm, a 25% absolute improvement in the MPR to 45% is considered a clinically meaningful minimum improvement in this study population. Therefore, proof of efficacy in the combination treatment arm will be declared if both of the following conditions are met:

- the mean of the posterior distribution of MPR is at least 45% and
- the posterior probability that the MPR is  $\geq 30\%$  is at least 90%

The posterior distribution of MPR will be derived from the prior distribution and all available data from the subjects in the FAS. A minimally informative unimodal Beta prior ([Neuenschwander et al 2008](#)) Beta(3/7, 1) and Beta(9/11, 1) will be used for canakinumab monotherapy and canakinumab in combination with pembrolizumab, respectively. Please refer to [Section 5.4.1](#) for details of prior distribution. The posterior mean of MPR will be calculated and the MPR rate with its corresponding two-sided exact binomial 95% confidence interval ([Clopper CJ and Pearson ES \(1934\)](#)) will be estimated in both the canakinumab monotherapy arm and canakinumab in combination with pembrolizumab arm. The posterior probability that  $MPR \geq 20\%$  and the posterior probability that  $MPR \geq 30\%$  will be calculated for canakinumab monotherapy arm and canakinumab in combination with pembrolizumab arm, respectively. Waterfall plot for percentage of residual viable tumor based on central review in canakinumab monotherapy arm and canakinumab in combination with pembrolizumab arm will be generated.

### **2.5.3 Handling of missing values/censoring/discontinuations**

Refer to [Section 2.5.2](#) for details on handling of intercurrent events. Subjects who have an unknown MPR status due to surgery not being performed (including lost to follow-up or withdrawal of study consent before surgery) or due to unevaluable MPR results will be considered as non-responders when estimating MPR rate.

### **2.5.4 Supportive analyses**

Additional supportive analysis for the primary analysis of MPR rate will be conducted by using an alternative strategy in handling of the intercurrent events.

The target population, study treatment, the primary variable and the summary measure will be the same as for the primary estimand except for handling of the intercurrent event of starting new antineoplastic therapy prior to surgery. Subjects will be included in the analysis for MPR

regardless of this intercurrent event (treatment-policy strategy). Same analyses will be done as for the primary estimand.

## **2.6 Analysis of secondary efficacy objective(s)**

The secondary efficacy objectives are to:

- To assess the MPR rate at the time of surgery
  - a) in the randomized pembrolizumab monotherapy arm based on central review
  - b) in all three randomized treatment arms based on local review
  - c) to estimate the difference in MPR and posterior probability that the difference in MPR is  $\geq 10\%$  between the randomized canakinumab + pembrolizumab combination arm and randomized pembrolizumab monotherapy arm based on central review
- To assess overall response rate in randomized subjects treated with canakinumab or pembrolizumab as monotherapy and in combination based on local review on the EOT visit
- To assess surgical feasibility rate in each treatment arm based on randomized subjects

### **2.6.1 MPR rate**

MPR rate (1) based on local review in all 3 treatment arms and (2) based on central review in pembrolizumab monotherapy arm will be assessed in the same patient population as the primary estimand. The intercurrent events and the strategy for handling intercurrent events will be the same as primary estimand.

MPR rate for all the above specified analyses will be summarized by treatment arm along with the two-sided exact binomial 95% confidence interval ([Clopper and Pearson 1934](#)). Waterfall plot for percentage of residual viable tumor based on central review in pembrolizumab arm will be generated.

The difference in MPR rate between canakinumab in combination with pembrolizumab and pembrolizumab single agent arm along with the two-sided exact 95% confidence interval based on [Chan and Zhang \(1999\)](#) will be summarized based on central review using the same patient population used in the primary analysis, including the strategy for handling intercurrent events. The posterior probability that the difference is 10% or greater in MPR rate will also be calculated in the following way: first, sampling from posterior distribution of MPR rate for each arm; then, calculating the sampling differences and probability that the difference is 10% or greater between the two arms. The minimal informative Beta prior Beta(9/11, 1) and Beta(3/7, 1) will be used for canakinumab in combination with pembrolizumab arm and pembrolizumab single agent arm, respectively.

## **2.6.2 Overall response rate (ORR)**

ORR is defined as the percentage of subjects in FAS with a best overall response of CR or PR, as per local review. The best overall response will be the observed response at the assessment performed on the EOT visit prior to surgery. ORR will be evaluated according to RECIST 1.1. Patients with a best overall response (BOR) of 'Unknown' per RECIST 1.1 will be considered as non-responders when estimating ORR. ORR and two-sided exact binomial 95% confidence interval ([Clopper and Pearson 1934](#)) will be presented by treatment group.

The BOR will be determined from response assessments undertaken while on treatment. In addition, only tumor assessments performed before the start of any further anti-neoplastic therapies will be considered in the assessment of BOR. A new anticancer therapy is defined as any secondary anticancer therapy (either systemic treatments, radiotherapy or surgery) received during or post study treatment.

## **2.6.3 Surgical Feasibility Rate**

Surgical feasibility rate is defined as the percentage of subjects in FAS who undergo surgery following study treatment. Surgical feasibility rate and two-sided exact binomial 95% confidence interval ([Clopper and Pearson 1934](#)) will be presented by treatment group.

## **2.7 Secondary objective: safety analyses**

All safety analyses will be performed based on the Safety Set and will be presented by treatment arm unless specified otherwise.

### **2.7.1 Adverse events (AEs)**

AE summaries will include all AEs occurring during on treatment period. All AEs collected in the AE (e)CRF page will be listed along with the information collected on those AEs e.g. AE relationship to study treatment, AE outcome etc. AEs with start date outside of on-treatment period will be flagged in the listings.

AEs will be summarized by number and percentage of subjects having at least one AE, having at least one AE in each primary system organ class (SOC) and for each preferred term (PT) using MedDRA coding by treatment arm. A subject with multiple occurrences of an AE will be counted only once in the respective AE category. A subject with multiple CTCAE grades (version 5.0) for the same preferred term will be summarized under the maximum CTCAE grade recorded for the event. AE with missing CTCAE grade will be included in the 'All grades' column of the summary tables.

In AE summaries, the primary system organ class will be presented alphabetically and the preferred terms will be sorted within primary SOC in descending frequency. The sort order for the preferred term will be based on their frequency in the canakinumab monotherapy arm.

The following adverse event summaries will be produced by treatment arm:

- Overview of adverse events and deaths
- AEs by SOC and PT (all AEs and AEs related to at least one study drug component)

- AEs by PT (all AEs and AEs related to at least one study drug component) and maximum CTC grade
- AEs leading to permanent discontinuation of one of the study drug component, AEs leading to canakinumab permanent discontinuation
- AEs leading to dose interruption
- AEs requiring additional therapy
- SAEs (all SAEs and SAEs related to at least one study drug component) and SAEs leading to fatal outcome.
- Summary of SAEs and non-SAEs with number of occurrences (an occurrence is defined as >1 day between start and prior end date of record of same preferred term).

### **2.7.1.1 Adverse events of special interest / grouping of AEs**

#### **Data analysis of AESIs**

An adverse event of special interest (AESI) is a grouping of adverse events that are of scientific and medical concern specific to compound canakinumab. These groupings are defined using MedDRA terms, SMQs (standardized MedDRA queries), HGLTs (high level group terms), HLT (high level terms) and PTs (preferred terms). Customized SMQs (Novartis MedDRA queries, NMQ) may also be used. A NMQ is a customized group of search terms which defines a medical concept for which there is no official SMQ available or the available SMQ does not completely fit the need. It may include a combination of single terms and/or an existing SMQ, narrow or broad. The groups are defined according to the MedDRA terms defined in the program Case Retrieval Strategy (CRS) document and will be summarized. The latest version of the CRS document available at the time of the analyses will be used. For each specified AESI, number and percentage of patients with at least one event of the AESI occurring during on treatment period will be summarized.

Summaries of these AESIs will be provided by treatment arm, (specifying grade, SAE, relationship, leading to treatment discontinuation, leading to dose interruption, hospitalization, death etc.).

A listing of all grouping levels down to the MedDRA preferred terms used to define each AESI will be generated.

AESI groupings are specified in the electronic Case Retrieval Strategy (eCRS). The latest version of the eCRS available at the time of the analysis will be used

### **2.7.2 Deaths**

Separate summaries for on-treatment and all deaths will be produced by treatment arm, system organ class and preferred term.

All deaths will be listed, and post treatment deaths will be flagged. A separate listing of deaths prior to starting treatment will be provided for all screened subjects.

### **2.7.3 Laboratory data**

When analyzing laboratory related date, all sources (central and local laboratories) will be combined. The summaries will include all assessments available for the laboratory parameters collected no later than 130 days after the last study treatment administration date (see [Section](#)

**2.1.3).** Grading of laboratory values will be assigned programmatically as per NCI Common Terminology Criteria for Adverse Events (CTCAE) version 5.0.

The following summaries will be produced for hematology and biochemistry laboratory data (by laboratory parameter and treatment):

- Worst post-baseline CTC grade (regardless of the baseline status). Each subject will be counted only for the worst grade observed post-baseline.
- Shift tables using CTC grades to compare baseline to the worst on-treatment value (hypo and hyper worst grade will be summarized separately if applicable)
- For laboratory tests where CTC grades are not defined, shift tables using the low/normal/high/(low and high) classification to compare baseline to the worst on-treatment value.
- If there are multiple assessments as baseline candidate, the central lab assessment will be defined as “baseline”. If there are multiple assessments from the central lab or the local lab, the worst assessment will be defined as “baseline.”

The following listings will be produced for the laboratory data:

- Listings of all laboratory data, with CTC grades and classification relative to the laboratory normal range. Lab data collected during the post-treatment period will be flagged.
- Listing of all CTC grade 3 or 4 laboratory toxicities

### **Liver function parameters**

Liver function parameters of interest are total bilirubin (TBL), ALT, AST and alkaline phosphatase (ALP). The number (%) of patients with worst post-baseline values as per Novartis Liver Toxicity guidelines will be summarized by treatment arm:

The following summaries will be produced:

- ALT > 3xULN
- ALT > 5xULN
- ALT > 10xULN
- ALT > 20xULN
- AST > 3xULN
- AST > 5xULN
- AST > 10xULN
- AST > 20xULN
- ALT or AST > 3xULN
- ALT or AST > 5xULN
- ALT or AST > 8xULN
- ALT or AST > 10xULN

- ALT or AST > 20xULN
- Total bilirubin (BILI) > 2xULN
- Total bilirubin (BILI) > 3xULN

AST and ALT =< ULN at baseline

- ALT or AST > 3xULN & BILI > 2xULN
- ALT or AST > 3xULN & BILI > 2xULN & ALP  $\geq$  2xULN
- ALT or AST > 3xULN & BILI > 2xULN & ALP < 2xULN

AST and ALT > ULN at baseline

- Elevated ALT or AST > 3xULN & BILI ( $>2x$  Bsl or 2x ULN)
- Elevated ALT or AST > 3xULN & BILI ( $>2x$  Bsl or 2x ULN) & ALP  $\geq$  2xULN
- Elevated ALT or AST > 3xULN & BILI ( $>2x$  Bsl or 2x ULN) & ALP < 2xULN

Elevated AST or ALT defined as: >3x ULN if =< ULN at baseline, or ( $>3x$  Bsl or 8x ULN) if > ULN at baseline.

In addition, a listing of all BILI, ALT, AST and ALP values for subjects with a post-baseline BILI > 2xULN, ALT > 3xULN or AST > 3xULN will be provided.

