5.1 Inclusion criteria

Subjects eligible for inclusion in this study must meet **all** of the following criteria:

1. Subjects must provide written informed consent prior to any screening procedures being performed.
2. Male and female patients \geq 18 years of age from the date of birth.
3. Histologically confirmed NSCLC stage IB-IIIA (per AJCC 8th edition), deemed suitable for primary resection by treating surgeon, except for N2 and T4 tumors (please refer to [Appendix 16.4](#)).
4. Subject must be eligible for surgery and with a planned surgical resection in approximately 4-6 weeks (after the first dose of study treatment).

5. A mandatory newly obtained tissue biopsy from primary site is required for study enrollment. An archival biopsy is also acceptable if obtained up to 5 months before first day of study treatment and if the subject did not go through antineoplastic systemic therapies between biopsy collection date and beginning of study treatment.
Note: Aspirates will not be accepted.
6. Subjects must have adequate organ function including the following laboratory values at the screening visit:
 1. Absolute neutrophil count (ANC) $\geq 1.5 \times 10^9/L$
 2. Platelets $\geq 100 \times 10^9/L$
 3. Hemoglobin (Hgb) $> 9 \text{ g/dL}$
 4. Creatinine clearance greater than 45 mL/min by calculation using Cockcroft-Gault formula
 5. Total bilirubin (TBIL) $\leq 1.5 \times$ upper limit of normal (ULN)
 6. Aspartate transaminase (AST) $\leq 3 \times$ ULN
 7. Alanine transaminase (ALT) $\leq 3 \times$ ULN
 8. Serum amylase $\leq 2 \times$ ULN or pancreatic amylase $\leq 1.5 \times$ ULN
7. Subject must have adequate cardiovascular and respiratory function to be submitted to surgical procedure as assessed per local clinical practice.
8. ECOG PS of 0 or 1.
9. Willing and able to comply with scheduled visits, treatment plan and laboratory tests.

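### Two SAP safety-table rules give wrong counts as written: patients with exactly one raised transaminase at baseline fit none of the six combined liver rows, and the respiratory-rate limits in Table 2-4 sit in the wrong columns

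*SAP*

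**What the plan says.** **Liver.** SAP 2.7.3 plans counts by arm of "worst post-baseline values as per Novartis Liver Toxicity guidelines". Fifteen rows have no baseline condition: four for ALT, four for AST, five for either enzyme and two for bilirubin. Six further rows combine transaminases with bilirubin, with and without a split on ALP. Three of them stand under "AST and ALT =< ULN at baseline" and three under "AST and ALT > ULN at baseline". The rows of the second block use the word *elevated*, which the SAP explains below them: "Elevated AST or ALT defined as: >3x ULN if =< ULN at baseline", with a second branch relative to baseline or 8 x ULN for an enzyme already above ULN. Their condition reads "Elevated ALT or AST > 3xULN & BILI ( $>2x$ Bsl or 2x ULN". Protocol 5.1, criterion 6, admits patients with "Aspartate transaminase (AST) $\leq 3 \times$ ULN" and "Alanine transaminase (ALT) $\leq 3 \times$ ULN".

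**Respiratory rate.** SAP Table 2-4 has one column for values above normal and one for values below normal. The respiratory-rate row gives a limit of less than 12 in the first and more than 25 in the second. SAP 2.7.4.2 then plans the number and percentage of patients with high and with low notable values, by arm.

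**The concern.** The two liver headings read as a partition of the patients, but they are not one. The opposite of both enzymes normal is at least one raised, not both raised. A patient with one raised enzyme who later has high transaminases and bilirubin would be missing from the table meant to show that combination. Protocol 6.5.2.1 describes this combination as possibly indicating severe drug-induced liver injury, and abnormal liver parameters are an adverse event of special interest for canakinumab (Protocol 10.1.1.1). Such cases are likely to be few in planned arms of 44, 44 and 22, so a single missing case could visibly change a row.

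For respiratory rate, a program that follows the column heads would report fast breathing as low and slow breathing as high. The summary covers the on-treatment period, which SAP 2.1.3.10 extends to 130 days after the last dose and which therefore includes time after surgery.

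**Working it through.** The plan states no figure on this point to reproduce. The check is whether the written rules classify patients correctly.

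**1. Coverage of the liver headings.** Each enzyme is either at or below ULN or above it, which gives 2 x 2 = 4 baseline patterns. I put the same post-baseline values through the six combined rows for each pattern. In multiples of ULN they are AST 2.5, ALT 9, bilirubin 2.5 and ALP 1.0, with baseline bilirubin 0.6. These are illustrative values.

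| Baseline AST / ALT (x ULN) | Heading met as written | Combined rows met as written | Combined rows met with *or* |
|---|---|---|---|
| 0.8 / 0.9 (both normal) | first | 2 | 2 |
| 1.2 / 1.5 (both raised) | second | 2 | 2 |
| 0.8 / 1.5 (only ALT raised) | none | 0 | 2 |
| 1.5 / 0.8 (only AST raised) | none | 0 | 2 |

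The two rows met are the overall row and the row with ALP below 2 x ULN. The result does not depend on the bilirubin wording discussed in step 5: at baseline 0.6 the SAP limit is 1.2 x ULN and both protocol limits are 2.0 x ULN, and 2.5 exceeds all of them.

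**2. Evidence of what was intended.** The definition of *elevated* has a branch for an enzyme at or below ULN at baseline, and the term is used only in the second block. As written, that block requires both enzymes above ULN, so the branch is reachable in 0 of 4 patterns. With *or* it is reachable in 2 of 4, exactly the two omitted ones. Protocol 6.5.2.1 makes a similar split with complementary groups: all of ALT, AST and TBIL normal, against any one of them elevated.

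**3. Size.** The share of patients with exactly one raised enzyme is not in the documents. Assumed shares of 5%, 10% and 20% of 110 planned patients give 5.5, 11 and 22 patients. With an assumed combined-event rate of 1% to 5% among them, the expected number of missed events runs from 5.5 x 0.01 = 0.055 (about 0.06) to 22 x 0.05 = 1.1, over all arms.

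**4. Respiratory rate.** Of the six rows in Table 2-4, the weight, systolic, diastolic, pulse and temperature rows agree with the column heads. Respiratory rate does not. A rate of 30/min meets the limit in the below-normal column and is counted as low; 10/min is counted as high; 16/min is not flagged. Exchanging the cells corrects both labels and leaves the set of flagged values unchanged.

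For the time after surgery: dose 2 is on Day 22, and surgery 4 to 6 weeks after dose 1 falls on Day 29 to Day 43, which is 7 to 21 days after dose 2. That leaves 130 - 21 = 109 to 130 - 7 = 123 on-treatment days after surgery.

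**5. Bilirubin condition, for reconciliation only.** The table gives the bilirubin limit for patients with raised baseline enzymes, in multiples of ULN. The SAP wording is read as either limb being enough, so the lower limit governs.

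| Baseline bilirubin | 0.3 | 0.5 | 1.0 | 1.5 |
|---|---|---|---|---|
| SAP 2.7.3 (2 x baseline or 2 x ULN) | 0.6 | 1.0 | 2.0 | 2.0 |
| Protocol 6.5.2.1 (2 x baseline and 2 x ULN) | 2.0 | 2.0 | 2.0 | 3.0 |
| Protocol Table 6-2 (2 x ULN) | 2.0 | 2.0 | 2.0 | 2.0 |

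The SAP agrees with Table 6-2 at or above ULN and differs below it. The two protocol rules also differ from each other, and only 6.5.2.1 counts a raised baseline TBIL as elevated. The liver guideline that the SAP cites is not in the documents, so this is an open question and not a demonstrated error.

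**The case against.** The strongest reply is that both slips are minor and easily recognised. The definition of *elevated* shows the liver intent, and nobody would take 30/min for a low respiratory rate. The affected patients are not lost. The example patient with only ALT raised is still counted in 6 of the 15 unconditional rows: ALT above 3 and 5, either enzyme above 3, 5 and 8, and bilirubin above 2 x ULN. The SAP also plans "a listing of all BILI, ALT, AST and ALP values for subjects with a post-baseline BILI > 2xULN", or with ALT or AST above 3 x ULN. Adverse-event, special-interest and laboratory shift tables offer further routes, and the protocol requires confirmed liver-injury cases to be reported as serious adverse events. All of that stands and limits the harm. None of it supplies the combined count by arm that the six rows are there to give, and a programmer who guesses the intent departs from the approved rule.

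It is also fair that the prevalence and event rates are assumptions and that 110 is the planned number. SAP section 1 records a halt to recruitment, and fewer patients would lower the figures. The 109 to 123 days assume dose 2 on Day 22 and surgery at 4 to 6 weeks, although later surgery is accepted. They describe the window only. Vital signs are taken at visits, so the range does not measure how many values are mislabelled.

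One further objection stands in part. With *or*, patients with one raised enzyme enter rows whose bilirubin condition is itself in question, so the heading change and the bilirubin query should be settled together. That is no reason to leave these patients uncounted.

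**Conclusion.** Both errors hold on the text as written. The combined liver rows omit 2 of the 4 baseline AST/ALT patterns, and 1 of the 6 rows in Table 2-4 has its direction reversed. The expected loss of combined liver events is small, 0.06 to 1.1 in total under the stated assumptions, and the true number cannot be derived from the documents. The effect is confined to descriptive safety tables. The primary MPR analysis, patient management and the set of respiratory values flagged as notable do not change. A swap in a single row is unlikely to be an artefact of reading the PDF, but the source table should be checked. The bilirubin difference is a matter to reconcile, and no threshold is endorsed here.

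**What to change.** 1. In SAP 2.7.3, replace *and* with *or* in the second liver heading, so that it covers patients with AST or ALT above ULN at baseline. All four patterns then fall under exactly one heading.
2. In SAP Table 2-4, exchange the two respiratory-rate cells.
3. Before the liver rows are programmed, the sponsor should reconcile the bilirubin condition in the raised-baseline rows, and the handling of raised baseline TBIL, with Protocol 6.5.2.1, Protocol Table 6-2 and the liver guideline that the SAP cites.

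The first two changes cost one word and two exchanged cells and need no new data; if outputs already exist, these tables need a rerun. The third needs a check against the sponsor guideline and, if the two protocol rules are meant to agree, a protocol clarification.
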